Est. Creatinine Clearance = [[140 - age (yr)]^*weight (kg)]/[72^*serum Cr(mg/dL)] (multiply by 0.85 for women)
Or
```

*Est. Creatinine Clearance = [[140-age(yr)]*weight (kg)]/[0.814* serum Cr(umol/L)]* (multiply by 0.85 for women)

⁴ In South Korea only, CgA assessment being discontinued in Q3 2022 due to lab kits shortage

⁵ For UK, serum pregnancy test is mandatory at baseline

During the Follow-up Phase, in both study arms laboratory assessments (hematology and blood chemistry) will be performed every 6 months (± 1 month).

8.5.3 **Pregnancy Test**

Women who receive Lutathera in the study, including those who crossed over to Lutathera and those re-treated with Lutathera, should not procreate during Lutathera treatment and until six months after the end of their last treatment with Lutathera, or until the end of treatment period of the study, whichever is longer. Women in the control arm should not procreate until the end of treatment period.

A pregnancy test (either on urine or blood) must be performed at baseline and within 14 days (preferably 7 days) prior to each Lutathera treatment for every female patient of childbearing potential (Section 5 and Appendix 1).

Ionizing radiations of lutetium (177Lu) oxodotreotide may potentially have temporary toxic effects on female and male gonads (decrease of inhibin-B and concomitant increase of FSH, suggesting radiation damage to Sertoli cells). Fertility is usually restored 12 to 18 months after treatment. The participant will be recommended to seek genetic consultation before starting treatment if the patient wishes to have children after treatment, which includes the option of cryopreservation of sperm or eggs before treatment starts.

For UK only:

A pregnancy test (blood) must be performed at baseline in both arms and within 7 days prior to the first Lutathera treatment. A urine or blood pregnancy test must be performed within 7 days prior to each Lutathera treatment for every female patient of childbearing potential (Section 5 and Appendix 1). A urine or blood pregnancy test must be performed in both arms at the end of the relevant systemic exposure to octreotide.

For Germany only:

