10.1.5 Adverse Events of Special Interest

AESI are defined as events (serious or non-serious) which are ones of scientific and medical concern specific to the Sponsor's product or program, for which ongoing monitoring and rapid

communication by the Investigator to the Sponsor is appropriate. Such events require further investigation in order to characterize and understand them.

AESI are defined based on the NETTER-1 study established AESI list as well as on the basis of an ongoing review of the safety data collected during Lutathera clinical programs and post marketing.

These potential risks deserve special attention even if they do not fulfill any of the seriousness criteria. AESI occurring in patients enrolled in both arms should be reported to the Sponsor for safety analysis following the reporting procedure and timelines for SAEs. During the treatment phase, all AESI need to be reported to the Sponsor irrespective of causality. During the follow-up phase, AESI need to be reported only if considered related to the study treatment except for all secondary hematological malignancies which need to be reported as AESI irrespective of causality.

The following AESI categories representing main risks of Lutathera and amino acid treatment are listed in Table 10-1.

Table 10-1. Adverse events of special interest

AESI categories
Hematotoxicity
Secondary hematological malignancies
Nephrotoxicityg
Cardiovascular and electrolyte disorders

Hematotoxicity: The main critical organ of Lutathera treatment is the bone marrow. Significant hematotoxicity, defined as Grade 2 or higher thrombocytopenia, or Grade 3 or 4 of anaemia, leuko-/neutropenia are considered dose-modifying toxicities in the study and must be reported as AESI when not strictly fulfilling the criteria of serious adverse events. Haematological toxicities regardless of severity must be reported as AESI if accompanied by clinical consequences, i.e., infections in the presence of leuko-/neutro-/lymphopenia, hemorrhages / purpuric lesions under thrombocytopenia that is not explained by another coagulation disorder, dyspnea / fatigue in the presence of anaemia not otherwise explained by the underlying carcinoid syndrome or other co-morbidity.

Secondary haematological malignancies: any secondary hematological malignancies, irrespective of causality, including MDS and acute myeloid leukemia, should be reported in every case, as AESI/SAE.

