2.8.1 Adverse events (AEs)

All adverse events (AEs), whether or not spontaneously reported by the patient, will be recorded starting from the signing of the ICF until the end of the randomized period/cross-over period/re-treatment period. During the Follow up Phase, only related serious adverse events and adverse events of special interest will be recorded, except for secondary hematological malignancies which will be recorded irrespective of relationship to Lutathera, Octreotide, and amino acid. The data provides information regarding relatedness to Lutathera, Octreotide and amino acid.

AEs that started or worsened during the on-treatment period (including randomized treatment, cross-over and re-treatment periods as defined in [Section 2.1.1.10](#)) is defined as treatment-emergent AEs (TEAE). The primary AE summaries will focus on all treatment-emergent AEs in the randomized treatment period that started or worsened during the randomized treatment

period, defined as from date of first administration of study treatment to 30 days after the date of the last actual administration of any study treatment in the randomized period before cross-over or retreatment. However, selected AE summaries will also be generated for cross-over and re-treatment periods separately. All AEs collected in the eCRF page will be listed along with the information collected e.g., AE relationship to study drug, AE outcome etc. In addition, each AE record in the listings will be flagged for its study period based on the start date.

AEs will be summarized by number and percentage of subjects having at least one AE, having at least one AE in each primary system organ class (SOC) and for each preferred term (PT) using MedDRA coding. A subject with multiple occurrences of an AE will be counted only once in the respective AE category. A subject with multiple CTCAE grades for the same preferred term will be summarized under the maximum CTCAE grade recorded for the event. AE with missing CTCAE grade will be included in the 'All grades' column of the summary tables.

In AE summaries, the primary SOC will be presented alphabetically and the PT will be sorted within primary SOC in descending frequency. For randomized period AE summaries, the sort order for the PT will be based on their frequency in the investigational arm.

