2.8.1.1 Adverse events of special interest / grouping of AEs

An adverse event of special interest (AESI) is a grouping of adverse events that are of scientific and medical concern specific to Lutathera.

Certain AESIs in this study are flagged in the eCRF by the investigator within the adverse event form, and the categories for Lutathera are included in [Table 2.8-1](#) below:

Table 2.8-1 Adverse events of special interest

AESI categories	Special consideration regarding grade
Immediate hematotoxicities	For Haematopoietic thrombocytopenia (SMQ), only include Grade >=2; for others only include Grade >=3.
Cardiovascular and Electrolyte Disorder	Only include Grade >=3.
Secondary hematological malignancies	
Nephrotoxicities	

To be conservative and align within the Lutathera NET program, these groupings are re-derived using MedDRA terms, SMQs (standardized MedDRA queries), HGLTs (high level group terms), HLT (high level terms) or PT. Customized SMQs (Novartis MedDRA queries, NMQ) may also be used. A NMQ is a customized group of search terms which defines a medical concept for which there is no official SMQ available or the available SMQ does not completely fit the need. It may include a combination of single terms and/or an existing SMQ, narrow or broad.

The grouping of AEs in AESI according to project standards will be specified in the electronic Case Retrieval Sheet (eCRS) and may be regularly updated. In addition, further rules regarding grade (see [Table 2.8-1](#)) will be implemented for the groupings of Hematotoxicities, Cardiovascular and electrolyte disorder.

Data analysis of AESIs

The re-derived AESI groupings using eCRS will be used in the analyses. Summaries of AESIs will be provided by treatment arm (specifying grade, seriousness, relationship, leading to treatment discontinuation, leading to dose reduction/interruption, death etc.). Separate summaries for AESIs will be provided for the randomized treatment period, and the overall study period. An analysis of time to first occurrence of each type of AESIs will be performed for the randomized treatment period. In addition, time to first occurrence will also be performed for long-term AESIs for patients who have been treated with Lutathera (see below for more details).

Time to first occurrence in the randomized treatment period

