Median time to first occurrence and 95% CI will be provided based on the Kaplan-Meier method. The event free rate at selected timepoints will be also estimated with 95% CI. In addition, Kaplan-Meier plots will be generated.

Time to first occurrence of AESI is defined as the time from the start of treatment to the start date of the first occurrence of any AE under the specific AESI in the randomized treatment period, i.e. time in days is calculated as (start date of first occurrence in the randomized treatment period) – (date of first dose of study treatment) +1. A participant will be censored if:

- The participant did not report any post-baseline AESI on or before the analysis cut-off date in the randomized treatment period.
- The participant discontinued randomized treatment without reporting the specific AESI in the randomized treatment period.
- The participant died without reporting the specific AESI in the randomized treatment period.
- The participant received a new anticancer therapy before reporting the specific AESI in the randomized treatment period.

The censoring date will be the earliest of the following dates: end date in the randomized treatment period, analysis cut-off, new anti-cancer therapy start date, death date and last contact date.

In addition, the median time to first occurrence for the subset of participants who experienced the event of interest will be calculated. Simple descriptive statistics, median, min and max as well as 25th percentile and 75th percentile, will be presented.

Time to first occurrence during the study

For long-term AESIs that can potentially occur after study treatment during follow-up, similar analysis as above will be repeated to consider all study periods, including randomized treatment period and any subsequent periods during the study. Such AESI includes secondary hematological malignancies and nephrotoxicity. This analysis is only for patients who have been treated with Lutathera, i.e., patients who were treated in the Lutathera arm and patients who did cross-over from the control arm. For cross-over patients, the time to first occurrence of AESI is counted from the start of cross-over to Lutathera instead of the randomized treatment and it will be summarized separately from the Lutathera arm.

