Events/censoring rules are same except that all assessments in the study will be used regardless of study periods. The censoring date will be the earliest of the following dates: analysis cut-off, death date and last contact date in the study.

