2.8.3 Laboratory data

The laboratory assessments require that blood samples for hematology and blood chemistry, and a urine sample for urinalysis are taken (see Table 8-2, Table 8-3, and Table 8-4 of the study protocol). Laboratory assessments will be performed at the investigational site.

The following laboratory parameters will be investigated and analyzed:

- (1) Haematology: White blood cells (WBC) with differential (i.e., Lymphocytes, Monocytes, Neutrophils, Eosinophils, Basophils), Platelets, Haemoglobin (Hb), Haematocrit, MCV
- (2) Blood chemistry: Blood urea nitrogen (BUN) or Urea, Serum creatinine, Uric acid, Albumin, Total bilirubin, ALP, AST/ASAT, ALT/ALAT, Gamma-GT, Sodium, Potassium, LDH, CgA (centralized assessment), Haemoglobin A1C (GlycoHb), fT4, Calcium, Magnesium, Fasting blood glucose, Thyrotropin, Creatinine clearance (calculated by the Cockroft-Gault formula)
- (3) Pregnancy test (if applicable)

On analyzing laboratory, data from all sources (central and local laboratories) will be combined. The summaries will include all assessments available for the lab parameter collected no later than 30 days after the last study treatment administration date (see [Section 2.1.1](#)). Separate

summaries will be generated for the randomized period, cross-over period, and re-treatment period.

Laboratory values outside normal ranges will be listed and flagged. The following flags will be used:

‘+’: ‘Higher than reference value’

‘-’: ‘Lower than reference value’

The respective parameter and the flagged value will be presented patient-wise by visit together with the reference values

The following summaries will be produced for hematology and biochemistry laboratory data (by laboratory parameter and treatment):

- Worst post-baseline CTC grade (regardless of the baseline status). Each subject will be counted only for the worst grade observed post-baseline.
- Shift tables using CTC grades to compare baseline to the worst on-treatment value
- For laboratory tests where CTC grades are not defined, shift tables using the low/normal/high/(low and high) classification to compare baseline to the worst on-treatment value.
- Box plots of laboratory values by scheduled time point.

The following listings will be produced for the laboratory data:

- Listings of all laboratory data, with CTC grades and classification relative to the laboratory normal range. Lab data collected during the post-treatment period will be flagged.

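### The whole-study nephrotoxicity curve in SAP 2.8.1.1 counts events of any cause while AEs are fully recorded but only investigator-judged related events in follow-up

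*SAP*

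**What the plan says.** SAP 2.8.1.1 repeats the time-to-first-occurrence analysis over the whole study for AESIs that may appear late, in patients treated with Lutathera in either arm: "Such AESI includes secondary hematological malignancies and nephrotoxicity". Cross-over patients are counted from their first Lutathera dose and summarised separately.

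- **Events.** They come from MedDRA groupings built from the recorded AEs, not from the investigator's flag: "The re-derived AESI groupings using eCRS will be used in the analyses". No relationship filter is stated, and Table 2.8-1 sets no grade limit for nephrotoxicities.
- **End of time at risk.** "The censoring date will be the earliest of the following dates: analysis cut-off, death date and last contact date in the study".
- **Recording on treatment.** SAP 2.8.1 says that all AEs "will be recorded starting from the signing of the ICF until the end of the randomized period/cross-over period/re-treatment period". Protocol 10.1.5 agrees: "During the treatment phase, all AESI need to be reported to the Sponsor irrespective of causality".
- **Recording in follow-up.** Protocol 10.1.5: "During the follow-up phase, AESI need to be reported only if considered related to the study treatment except for all secondary hematological malignancies". Protocol 8.5.1, the footnotes to Tables 8-3 and 8-4, and SAP 2.8.1 carry the same limit and the same single exemption.
- **Laboratory data.** Protocol 8.5.2 provides that in follow-up "in both study arms laboratory assessments (hematology and blood chemistry) will be performed every 6 months", and Table 8-2 includes creatinine. SAP 2.8.3 limits their use: "The summaries will include all assessments available for the lab parameter collected no later than 30 days after the last study treatment administration date". Later values are listed and flagged.

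**The concern.** A Kaplan-Meier curve assumes that an event of the stated kind would be recorded for as long as the patient is in the risk set. For nephrotoxicity that stops being true when follow-up begins. A renal event that the investigator attributes to age, diabetes or the tumour counts while AEs are fully recorded. The same event in follow-up is never recorded, although the patient's time still counts. The curve can flatten because the recording rule changed, not because the hazard fell.

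This matters because Protocol 4.5 names bone marrow and kidney as the sites of highest radiation risk, and Protocol 3.5 gives long-term safety as a purpose of follow-up. The trial is open-label (Protocol 6.4), so relatedness is judged with knowledge of treatment.

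**Working it through.** The plan states no figure for this analysis, so there is nothing to reproduce. The first check sets recording against time at risk.

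| | Secondary haematological malignancy | Nephrotoxicity |
|---|---|---|
| Randomized, cross-over and re-treatment periods | any cause | any cause |
| Follow-up | any cause | related only |
| Time at risk ends | cut-off, death or last contact | cut-off, death or last contact |

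The method is coherent in the first column. In the second, the event definition changes partway and the risk set does not.

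**Share of time at risk under related-only recording**, T2/(T1 + T2), where T1 is all-cause recording and T2 is follow-up, taken at its three-year maximum (Protocol 3.5):

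- Cross-over: end-of-treatment visit at week 28 (Protocol 3.3). 156/(28 + 156) = 156/184 = 85%.
- Lutathera arm, stopping at week 72 plus 30 days: T1 = (504 + 30)/365.25 = 1.46 years. 3/4.46 = 67%.
- Lutathera arm, at the 30-month median PFS assumed in SAP 3: T1 = 2.5 years. 3/5.5 = 55%.

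**Illustration of the effect.** Assume a constant all-cause renal event hazard λ and a share r of follow-up events judged related. Neither is in the documents.

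- All-cause incidence = 1 − exp[−λ(T1 + T2)]
- Reported incidence = 1 − exp[−λ(T1 + r·T2)]

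For cross-over, T1 = 28 × 7/365.25 = 0.537 years. With λ = 0.05 per year and r = 0.5, all-cause incidence is 1 − exp(−0.05 × 3.537) = 16.2% and reported incidence is 1 − exp(−0.05 × 2.037) = 9.7%.

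| λ = 0.05 per year | All-cause | Reported, r = 0.25 | r = 0.50 | r = 0.75 |
|---|---|---|---|---|
| Cross-over, 28 weeks | 16.2% | 6.2% | 9.7% | 13.0% |
| Lutathera arm, 72 weeks + 30 days | 20.0% | 10.5% | 13.8% | 16.9% |
| Lutathera arm, 30 months | 24.0% | 15.0% | 18.1% | 21.1% |

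Over λ from 0.02 to 0.10 per year and r from 0.25 to 0.75, reported incidence is 0.37 to 0.82 of all-cause for cross-over, 0.51 to 0.86 for 72 weeks plus 30 days, and 0.60 to 0.89 for 30 months. The gap is zero only if every follow-up event is judged related (r = 1).

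**The other reading.** Suppose the target is related nephrotoxicity and the related share is r throughout. The target is then 1 − exp[−λr(T1 + T2)]. With λ = 0.05 and r = 0.5:

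- Cross-over: 1 − exp(−0.025 × 3.537) = 8.5%, against 9.7% reported.
- Lutathera arm, 72 weeks + 30 days: 1 − exp(−0.025 × 4.462) = 10.6%, against 13.8% reported.

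The same curve is too low for one target and too high for the other.

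**The case against.** Several points against a stronger version of this concern stand.

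- **A reader might infer that late renal risk is simply understated.** That depends on the target. Protocol 10.1.5 leaves renal failure of obvious non-drug origin out of the investigator's AESI report, so a related-event target is arguable. Under it the fault is over-counting on treatment. The SAP does not choose: it re-derives the grouping from all recorded AEs.
- **A reader might take 85% as general.** It is a ceiling for cross-over patients who reach three years; Protocol 3.3 ends their follow-up at end of study if that comes first. In the Lutathera arm, all-cause recording continues with octreotide to progression, or to week 72 after the PFS analysis. The fourth dose is at week 24, so week 72 is 48 weeks later, and the assumed 30-month median (about 130 weeks) is about 106 weeks later. All-cause recording also resumes during re-treatment.
- **A reader might infer that the trial cannot answer its long-term renal question.** The documents do not support that. The laboratory cut-off runs from the last dose of any component (SAP 2.1.1.5), so Lutathera-arm creatinine summaries continue while octreotide does. Later grade 3 or 4 values are listed. SAP 2.8.1.1 also plans AESI summaries by relationship and a randomized-period curve that ends with that period.

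These points limit the size but do not remove the mismatch. The randomized-period curve does not cover cross-over exposure, and nothing labels or adjusts the whole-study curve. Protocol 9.1.1 lists AEs among data collected after discontinuation, but by the schedule in Tables 8-3 and 8-4, whose footnotes impose the related-only limit. The follow-up sentence in SAP 2.8.1 could be read as applying relatedness to serious events only; its exemption for haematological malignancies would then have no purpose, and the protocol is explicit.

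**Conclusion.** The point holds as a mismatch of definitions. Followed as written, the plan gives a whole-study nephrotoxicity curve that is all-cause at first and related-only later, with one risk set throughout. The direction of error follows from the target chosen. The size cannot be given: the documents contain neither a renal event rate nor a related share, and the incidences shown rest on assumed values of both, a constant hazard and a full three years of follow-up. The exposure to the problem can be bounded. It is greatest for cross-over patients (at most 85% of time at risk) and smaller in the Lutathera arm (67% or 55% in the two cases worked).

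Secondary haematological malignancies are not affected. The display is descriptive and no hypothesis test depends on it, but it concerns one of the treatment's main known risks, so it should be corrected.

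**What to change.** In SAP 2.8.1.1, use one event definition per nephrotoxicity curve:

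- (a) an all-causality curve censored when all-cause AE recording ends, with follow-up events shown separately and labelled as related only; or
- (b) a curve restricted to related events throughout and labelled as such. SAP 2.8.1 confirms that relationship is collected.

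Under (a), state how re-treated patients are handled, since all-cause recording can stop and resume.

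In SAP 2.8.3, add a follow-up-period summary of the six-monthly serum creatinine: worst CTCAE grade and percentage change from baseline, for example the number of patients with an increase of 40% or more. Protocol Table 6-4 already uses that figure; here it is only a descriptive cut-off. Creatinine clearance should be secondary. Tables 8-3 and 8-4 show no weight at the six-monthly visits, so where SAP 5.3 has to derive clearance it would carry an older weight forward. An absolute limit of 40 mL/min is also a poor event definition, because patients may enter at that value and a trivial fall would count.

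The cost is SAP wording and one or two extra tables, with no new data or visits. The laboratory display will also pick up renal decline unrelated to the drug, which a footnote should say.

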1.1 Background

Neuroendocrine tumors (NET) are rare malignant neoplasms that can arise throughout the body, and account for approximately 1% of all human tumors. NETs have been classified according to their embryonic origin as foregut, midgut, or hindgut NETs. The World Health Organization (WHO) staging system classifies gastroenteropancreatic NET (GEP-NET) based on primary tumor localization, size, mitotic activity, invasiveness, and functional status (Klöppel, 2011). Despite certain common morphological and immunohistochemical features, there is significant heterogeneity in the prognosis and treatment strategies according to the primary site, histological differentiation (poorly or well-differentiated) and stage. Histologic differentiation and proliferative activity are the strongest predictors of survival. In terms of site of origin, the majority (50-70%) of NETs diagnosed in Western countries are gastrointestinal NETs (Modlin, Lye, & Kidd, 2003). Of 270 NETs originating in the midgut or hindgut, 62% (5- year survival rate (YSR), 95.2%) were Grade 1, 32% (5-YSR 82.0%) were Grade 2, and 6% (5-YSR, 51.4%) were Grade 3 NETs (Jann, et al., 2011). 50-70% of NETs of unknown origin have been reported to be well-differentiated (Catena, et al., 2011) and have a similar behavior and prognosis to midgut NETs (Kirshbom, Kherani, Onaitis, Feldman, & Tyler, 1998).

Surgical resection of the primary and metastatic lesions remains the mainstay of treatment, and the only way to obtain a cure. However, resection is often not possible as NETs are frequently detected in a more advanced tumor stage (Yao, et al., 2008).

In patients with inoperable NET, the treatment goal is to prolong survival, improve and maintain quality of life, to control tumor growth, and to control secretory symptoms (if the tumor is functional). Somatostatin analogs (SSAs) octreotide long-acting 30 mg (Sandostatin[®] LAR[®]) or lanreotide ATG 120 mg (lanreotide ATG, SOMATULINE[®] DEPOT or SOMATULINE[®] AUTOGEL[®]) have become the mainstay of treatment in patients with low- or intermediate-grade GEP-NET.

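### Long-term AESI risk in Lutathera-treated patients is estimated by Kaplan-Meier with deaths censored, so the complement of the reported event-free rate overstates the cumulative incidence of recorded events, modestly at the documents' own survival figures

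*SAP*

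**What the plan says.** SAP 2.8.1.1 describes two analyses of time to first AESI. For the randomized treatment period it says "Median time to first occurrence and 95% CI will be provided based on the Kaplan-Meier method", adds "The event free rate at selected timepoints will be also estimated with 95% CI", and calls for Kaplan-Meier plots. One of its listed reasons for censoring is "The participant died without reporting the specific AESI in the randomized treatment period".

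For AESIs that can arise long after treatment, a "similar analysis as above will be repeated to consider all study periods, including randomized treatment period and any subsequent periods during the study". On which events are covered: "Such AESI includes secondary hematological malignancies and nephrotoxicity". Only patients who received Lutathera are included: those treated in the Lutathera arm, and control patients who crossed over. The latter are counted from the start of cross-over and summarized separately. On censoring: "The censoring date will be the earliest of the following dates: analysis cut-off, death date and last contact date in the study".

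The same section plans other AESI output: "Separate summaries for AESIs will be provided for the randomized treatment period, and the overall study period". SAP 2.8.1 summarizes AEs by number and percentage of subjects, and SAP 2.8.2 summarizes deaths by period and lists them. Neither document plans a cumulative incidence function or any other competing-risk method for AESIs.

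**The concern.** Censoring is harmless when the censored patient could still have the event later and is like those who remain under observation. A dead patient cannot develop leukemia or renal failure. Censoring at death hands that patient's future risk to the survivors, so the curve describes a setting in which nobody dies. If the event-free rate at a time point is subtracted from 100% and taken as the proportion of patients who have the event by then, the answer is too high, and the gap grows as deaths accumulate.

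These are the delayed risks that the analysis exists to describe. Protocol 10.1.5 singles out marrow and kidney as critical organs. Follow-up runs to at least 4 years after the last randomization (Protocol 9.2), which gives the gap time to open.

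**Working it through.** The documents give no AESI risk or mortality assumption for this analysis, so there is no planned figure to reproduce.

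**Direction.** On the same data, both estimators add up (number still event-free) × (AESIs ÷ number at risk). Kaplan-Meier weights each step by AESI-free survival with deaths ignored. Aalen-Johansen weights it by survival free of both AESI and death, which can never be larger. So 1−KM is at or above the cumulative incidence of recorded events whatever the hazards, and equal only if no death precedes an AESI.

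**Inputs for size.**
- Mortality: Protocol 1.1 gives 5-year survival by grade for a midgut and hindgut series: "32% (5-YSR 82.0%) were Grade 2, and 6% (5-YSR, 51.4%) were Grade 3 NETs". It is treated here as survival without the AESI.
- True risk: 2% at 4 years (assumed). This is the upper end of the 1.5 to 2% that Protocol 4.5 gives for delayed marrow toxicity, used as a proxy.
- Constant hazards (assumed): *a* for the AESI, *d* for death.

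**Formulas.**
- CIF(t) = a/(a+d) × [1 − exp(−(a+d)t)]
- 1−KM(t) = 1 − exp(−a·t)

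Fix CIF(4) = 0.02, solve for *a*, and read off 1−KM(4).

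*G2.* d = −ln(0.820)/5 = 0.0397 per year, so 4-year survival is exp(−4 × 0.0397) = 0.853. Solving gives a = 0.00547, and 1 − exp(−4 × 0.00547) = 2.16%.

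*G3.* d = −ln(0.514)/5 = 0.1331, so 4-year survival is 0.587. Solving gives a = 0.00653, and 1 − exp(−4 × 0.00653) = 2.58%.

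| 4-year survival | Source | True risk | 1−KM | Excess, points | Ratio |
|---|---|---|---|---|---|
| 85.3% | Protocol 1.1, G2 | 2.0% | 2.16% | 0.16 | 1.08 |
| 58.7% | Protocol 1.1, G3 | 2.0% | 2.58% | 0.58 | 1.29 |
| 50% | assumed | 2.0% | 2.77% | 0.77 | 1.38 |
| 40% | assumed | 2.0% | 3.05% | 1.05 | 1.52 |
| 30% | assumed | 2.0% | 3.43% | 1.43 | 1.71 |

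**Sensitivity.**
- A commoner AESI with an assumed true 4-year risk of 10% would read as 10.8% (G2) or 12.8% (G3).
- If the AESI hazard begins only after 2 years (assumed), a true 2% at 4 years reads as 2.25% (G2) or 2.97% (G3).

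**Simulation.** In 3,000 simulated arms of 148 patients with a true 5-year risk of 2%, mean 1−KM was 2.20% (G2 mortality) and 2.75% (G3), against Aalen-Johansen means of 2.00% and 2.02%. The closed form at 5 years gives 2.20% and 2.73%.

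**Against sampling error.** The planned Lutathera arm has 148 patients (SAP 3). Two percent of 148 is about 3 events, and 3/148 has an exact 95% CI of 0.4% to 5.8%. An excess of 0.2 to 0.6 points lies well inside it.

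**The case against.** The best defence is that the SAP reports an event-free rate and does not call its complement patient risk. Net event-free probability is a recognised descriptive quantity, and the planned counts and percentages of patients with AESIs do not carry this bias. This stands in part. However, the SAP does not say that risk in the absence of death is its target, and does not argue that death and AESI are independent, which that reading needs. The crude percentages ignore follow-up time, so they do not replace a risk at a stated time.

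The second defence is size, and it stands: at the documents' survival figures the excess is a fraction of a point on about 3 expected events.

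A reader might also infer four stronger things that the documents do not support:

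- *That mortality here is known to be high and the overstatement correspondingly large.* Protocol 4.5 says only that distant or grade 3 disease has a poor outlook. Four-year survival of 50% or less is an assumption. Equally, the Protocol 1.1 series is not restricted to advanced disease, so mortality in this trial may be worse than it shows.
- *That reported nephrotoxicity must exceed the true all-cause risk.* In follow-up, AESIs other than secondary hematological malignancies are recorded only if related to treatment (Protocol 10.1.5, SAP 2.8.1). That pushes the other way, so the net direction against all-cause risk is uncertain.
- *That a comparison between groups is distorted.* The Lutathera-arm and cross-over displays have different time origins, are separate, and are not tested against each other.
- *That the randomized-period analysis needs the same change.* It is an on-treatment analysis that also censors at treatment discontinuation and at new anticancer therapy. Making death a competing event would leave those censorings in place.

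**Conclusion.** The point holds as a low-priority improvement to a descriptive safety output. In the analysis of time to first occurrence during the study, deaths are censored, so one minus the reported event-free rate is at or above the cumulative incidence of recorded AESIs. That direction needs no assumption.

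The size rests on constant hazards, a 2% true 4-year risk and borrowed mortality. It is 8 to 29% relative, or 0.2 to 0.6 points, at the documents' background survival, and 0.8 to 1.4 points if 4-year survival is 50% to 30%. The excess may differ between the Lutathera-arm and cross-over displays if mortality differs, which matters only to someone who compares them informally. Type I error, power and the primary PFS result are untouched. For secondary malignancy the bias runs against Lutathera.

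**What to change.** In SAP 2.8.1.1, for the analysis of time to first occurrence during the study only, make Aalen-Johansen cumulative incidence with 95% CI at the selected time points the main estimate, with death without the AESI as a competing event. Show it separately for the Lutathera arm and for cross-over patients, as already planned. Keep the Kaplan-Meier curve as a supplementary display, labelled as risk in the absence of death. For nephrotoxicity, add a footnote that only related events are recorded in follow-up.

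The same edit can settle a wording matter. The SAP says that the event and censoring rules match those of the randomized-period analysis, yet the long-term list of censoring dates omits the start of new anticancer therapy. It should say whether that still censors.

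The cost is one changed output from standard software. Death dates are already collected and already enter the derivation, so no new data are needed.
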